5.5 Treatment after the End of the Study

Subjects will not receive any additional treatment with the study drug from the Sponsor after completion of the study because the indication being studied is not life threatening or seriously debilitating and other treatment options are available.

The Investigator is responsible for ensuring that consideration has been given to the post study care of the subject's medical condition, whether or not the Sponsor is providing specific post-study drug.

5.6 Prior and Concomitant Therapy

For rollover subjects, any medication (including over the counter or prescription medication, vitamins and/or herbal supplements) administered to the subject at the time of enrollment and during the study must be recorded on the CRF along with the reason for use. For direct-enrolling subjects, any medication (including over the counter or prescription medication, vitamins and/or herbal supplements) administered to the subject up to 30 days before the Screening visit, at the time of enrollment, and during the study must be recorded in the CRF along with the reason for use. The information to be recorded must also include name of the medication (generic name, as a general rule), dose, frequency, administration routes, and dates of the first and last dose, as applicable.

The Medical Monitor should be contacted if there are any questions regarding concomitant or prior therapy.

5.6.1 Permitted Medications and Nondrug Therapies

Concomitant medications for medical treatment of other conditions are allowed under the condition that the dosage and administration of these treatments is not planned to change from the Baseline visit to the completion of the treatment phase (Week 48) and that the medication is not a prohibited medication as described in the Exclusion Criteria (Section 5.6.2).

In the event of skin infection, topical antibacterial agents with the exception of gentamicin and neomycin sulfate can be applied to the infected area; however, study drug must not be applied to the area until the skin infection is healed.

Nonmedicated emollients that do not contain salicylic acid may be used on nonlesional skin but the subject (or caregiver) should wait at least 30 minutes after applying study drug before applying nonmedicated emollients; emollients should not be applied to lesional skin during treatment. The same emollient should be used throughout the subject's participation in the study.

Any emollient used during the study must be recorded as a concomitant medication.

5.6.2 Prohibited Medications and Nondrug Therapies

Medications and nondrug therapies that are prohibited throughout the study duration are as follows:

- DUPIXENT® (dupilumab) injection, or any monoclonal antibody product that becomes approved for AD during the course of the trial
- Oral, injectable, and suppository preparations of corticosteroids. Eye drops and nasal preparations are allowed. Inhaled preparations are allowed when used for a stable condition and stable dose for > 28 days before Baseline and are continued at the same dose throughout the study.
- Oral preparations and injections of immunosuppressants (cyclosporine, methotrexate, azathioprine, tacrolimus, JAK inhibitors, etc.).
- Excessive sun exposure, tanning booth, other ultraviolet light source and phototherapy including psoralen and ultraviolet A therapy or is unwilling to minimize natural and artificial sunlight exposure.
- Treatment with antivirals with the exception of short-term treatment for acute upper respiratory viral infections (i.e., influenza) or viral suppressive therapy for a history of recurrent herpes labialis or genital herpes.
- EUCRISA® (crisaborole) and any other phosphodiesterase 4 inhibitor.
- Tacrolimus ointment and pimecrolimus cream.
- Topical JAK inhibitors.
- Topical corticosteroids that are classified as low potency (e.g., desonide, hydrocortisone), medium or high potency (e.g., fluocinonide, triamcinolone acetonide) or super-high potency (e.g., clobetasol propionate). Eye drops and nasal preparations are allowed.
- Over the counter or herbal medicines for AD (topical and oral preparations). If subjects are using emollients, they may continue to use the same emollient on nonlesional skin during the study. Emollients containing salicylic acid are prohibited during the study.
- Oral, injectable, or intravenous antibiotics or antifungal medications.
- Topical doxepin or topical antibiotics.

NOTE: Oral doxepin is allowed for treatment of depression if subject has been on a stable dose (4 weeks) at Screening

- Antihistamines/antiallergics (oral, topical and injections): diphenhydramine, chlorpheniramine maleate, hydroxyzine.

NOTE: The following antihistamines are allowed from Screening throughout the treatment period: loratadine, fexofenadine hydrochloride, cetirizine hydrochloride. Subjects are allowed to switch from non-allowed antihistamines to allowed antihistamines during Screening but must be on a stable dose for 7 days prior to Baseline.

- Any investigational products or procedures.

A list of prohibited medications, emollients and nondrug therapies may be provided as a separate document. If a subject chooses to treat scalp with study drug, then medicated shampoos are prohibited for use. Emollients containing salicylic acid are prohibited.

6 Study Assessments and Procedures

Study procedures and assessments are summarized in the Schedule of Assessments ([Table 1](#)) and in Section [7](#). Adherence to the study design requirements, including those specified in the Schedule of Assessments are essential and required for study conduct. Protocol waivers or exemptions are not allowed, except for immediate safety concerns.

For rollover subjects, age is determined as age at the time of consent in the parent study. For direct-enrolling subjects, age is determined as age at the time of consent in this study. In both cases, the determined age will remain the same throughout the duration of this study for the purposes of completing all study assessments.

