- Excessive sun exposure, tanning booth, other ultraviolet light source and phototherapy including psoralen and ultraviolet A therapy or is unwilling to minimize natural and artificial sunlight exposure.
- Treatment with antivirals with the exception of short-term treatment for acute upper respiratory viral infections (i.e., influenza) or viral suppressive therapy for a history of recurrent herpes labialis or genital herpes.

c. From 14 days prior to Baseline:

- EUCRISA® (crisaborole) and any other PDE4 inhibitor.
- Tacrolimus ointment and pimecrolimus cream.
- Topical JAK inhibitors.
- Topical corticosteroids that are classified as medium or high potency (e.g., fluocinonide, triamcinolone acetonide) or super-high potency (e.g., clobetasol propionate). Eye drops and nasal preparations are allowed.
- Over the counter or herbal medicines for AD (topical and oral preparations). If subjects are using emollients, they may continue to use the same emollient on nonlesional skin during the study. Emollients containing salicylic acid are prohibited during the study.

d. From 7 days prior to Baseline:

- Topical corticosteroids that are classified as low potency (e.g., desonide, hydrocortisone).
- Oral, injectable, or intravenous antibiotics or antifungal medications.
- Topical doxepin, topical gentamicin, or topical neomycin sulfate.

NOTE: Oral doxepin is allowed for treatment of depression if subject has been on a stable dose (4 weeks) at Screening

- Topical products containing urea, except for the treatment of follicular events.
- Antihistamines/antiallergics (oral, topical and injections): diphenhydramine, chlorpheniramine maleate, hydroxyzine.

NOTE: For direct-enrolling subjects, the following antihistamines are allowed from Screening throughout the treatment period: loratadine, fexofenadine hydrochloride, cetirizine hydrochloride. Subjects are allowed to switch from non-allowed antihistamines to allowed antihistamines during Screening but must be on a stable dose for 7 days prior to Baseline.

e. The subject has received an investigational product within the following time period prior to the first dosing day in the current study: Minimum of 30 days or 5 half-lives of the investigational product (whichever is longer).

For All Subjects (Rollover Subjects and Direct-Enrolling Subjects):

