4.5.1 Reasons for Withdrawal from the Study

Study drug will be discontinued and the subject withdrawn from the study for any of the following reasons:

- Subject has an AE that is considered to be related to study drug or procedures AND is severe enough to warrant treatment discontinuation, as determined by the Investigator (Section 8.1).
- Pregnancy
- Any Grade 3 or 4 AE, based on Cancer Institute Common Terminology Criteria for Adverse Events (CTCAE) criteria, considered causally related to study drug (Section 8.2.2)

Study drug may be discontinued and the subject withdrawn from the study for any of the following reasons:

- Subject requires concurrent prohibited medication during the study (Section 5.6.2). Nonmedicated emollients that do not contain salicylic acid may be used on nonlesional skin but the subject (or caregiver) should wait at least 30 minutes after applying study drug before applying nonmedicated emollients; emollients should not be applied to lesional skin during treatment. The same emollient should be used throughout the subject's participation in the study.

NOTE: If, in the opinion of the Investigator and the study Medical Monitor, such medication will not interfere with the conduct or interpretation of the study or compromise the safety of the subject, then the subject may continue to receive study drug.

- Subject noncompliance
- Investigator noncompliance
- Discontinuation of the study at the request of the Sponsor, regulatory agency, or an Institutional Review Board (IRB)/Independent Ethics Committee (IEC).

If a subject meets a withdrawal criterion during treatment, an Early Termination visit will be required (Section 7.7).

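### Protocol 5.6.2 bans all topical antibiotics while 5.6.1 allows most of them on infected skin, so permitted infection care can be logged as a deviation

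*Protocol*

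**What the plan says.** Four parts of the protocol and one of the SAP bear on this.

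- **Protocol 5.6.1 (permitted therapies).** For skin infection, "topical antibacterial agents with the exception of gentamicin and neomycin sulfate can be applied to the infected area". Study drug is withheld from that area until it heals. Earlier in the section, medication for other conditions is allowed if its dosing is not planned to change and "the medication is not a prohibited medication as described in the Exclusion Criteria (Section 5.6.2").
- **Protocol 5.6.2 (prohibited throughout the study).** One bullet reads "Topical doxepin or topical antibiotics". Another bars "Oral, injectable, or intravenous antibiotics or antifungal medications".
- **Protocol 4.3, exclusion criterion 13d.** For direct-enrolling subjects, the 7-day washout before Baseline names "Topical doxepin, topical gentamicin, or topical neomycin sulfate".
- **Protocol 4.5.1 and 5.6.** A possible reason for withdrawal is "Subject requires concurrent prohibited medication during the study", with a reference to 5.6.2. If the Investigator and Medical Monitor see no interference with the study and no safety risk, "then the subject may continue to receive study drug". Section 5.6 adds: "The Medical Monitor should be contacted if there are any questions regarding concomitant or prior therapy".
- **SAP 9.2.** Deviations are tabulated as major or minor and listed by subject. There is no rule for topical antibiotics.

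**The concern.** The same act, putting a topical antibiotic such as one outside the two named agents on infected skin, is allowed by one section and forbidden by the next. The situation is foreseeable. Section 5.6.1 plans for it, Appendix 1 lists a tendency to skin infection among the minor diagnostic criteria for atopic dermatitis, and section 1.1.1 names impetigo among the more frequent adverse events in the two Phase 2b studies (one in atopic dermatitis, one in psoriasis).

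Three things are at stake. A site may withhold infection care that the protocol means to allow. A subject may be considered for withdrawal without need, and section 4.5 says withdrawn subjects are not replaced. And two sites giving identical treatment may report it differently, one as a deviation and one not.

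**Working it through.** The plan has no figure to reproduce here, so the check is a comparison of text.

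| Place | Topical gentamicin, neomycin | Other topical antibiotics on infected skin | Systemic antibiotics |
|---|---|---|---|
| 5.6.1 | not permitted | permitted | not addressed in the infection sentence |
| 5.6.2 | prohibited | prohibited | prohibited |
| 4.3, criterion 13d (washout) | excluded | not excluded | excluded |

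The conflict lies in the middle column. Four readings might remove it.

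1. **5.6.1 means antiseptics only.** This fails. Gentamicin and neomycin are antibiotics, and there would be no reason to carve them out of a permission that did not cover antibiotics.
2. **5.6.1 is an implied exception to 5.6.2.** This is plausible as intent but is not written. Section 5.6.2 states its exceptions where it wants them: for antivirals, inhaled corticosteroids, oral doxepin and certain antihistamines. The topical antibiotic bullet has none and does not refer back to 5.6.1.
3. **The cross-reference in 5.6.1 decides it.** It does not. It names the exclusion criteria but gives the number 5.6.2, and those two lists differ on exactly this point. The proviso also concerns medication for other conditions and does not expressly govern the infection sentence.
4. **A separate list decides it.** The end of 5.6.2 says only that such a list may be provided. The protocol text stays in conflict either way.

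Taken literally and alone, 5.6.2 leaves no compliant antibiotic for infected skin, because the topical and the systemic routes are both closed.

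**Size.** The documents give no rate of topical antibiotic use. With N = 961 (the enrolment ceiling in Protocol 10.2) and an assumed share p of subjects treated this way, the number affected is N × p:

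- p = 1%: 961 × 0.01 = 9.61, about 10 subjects
- p = 5%: 961 × 0.05 = 48.05, about 48 subjects

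These are the subjects whose deviation status would depend on which section is applied. They are not a forecast of deviations recorded.

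**The case against.** The best counter-argument is that a specific rule qualifies a general one. Section 5.6.1 covers one situation and one site, names its exceptions and gives a handling rule; 5.6.2 is a general list. On that reading a sensible site would never see a conflict. The reading is reasonable and may well be what was meant, but it has to be supplied by the reader, and the protocol does not supply it.

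A second argument is that the deviation consequence is inferred. This is true: no sentence makes use of a prohibited medication a deviation, whereas missed doses (5.1.5.3) and assessments missed at virtual visits (6.5) are expressly so labelled. The data management plan and any separate list of prohibited medications are not available to check. The claim is therefore only that such use *can* be logged as a deviation. That is a fair expectation where a single missed daily dose already counts as one.

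A third is that withdrawal is discretionary and goes through the Medical Monitor. This stands, and it limits the harm. It settles whether the subject stays on drug but not how the use is classified.

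A fourth is that criterion 13d is a washout for direct-enrolling subjects, and a washout list may properly differ from an on-study list. This also stands. Criterion 13d shows that the cross-reference is ambiguous; it does not by itself show which section is right.

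Last, no analysis set depends on deviations. The ITT population is all enrolled subjects (Protocol 10.3, SAP 8) and there is no statistical testing (SAP 6). This is accepted in full.

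**Conclusion.** The concern holds. Two operative rules in adjacent sections contradict each other, and 5.6.2 is wrong as written if 5.6.1 is meant to apply. The effect is confined to conduct, possible avoidable withdrawals and the deviation table and listing. It arises only for skin infections treated with a topical antibiotic other than gentamicin or neomycin. The range of 10 to 48 subjects rests wholly on the assumed 1% to 5% and on enrolment reaching its ceiling. No effect on the ITT efficacy or safety results is shown. It should be corrected because the contradiction is plain and the repair is small.

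**What to change.** - **Protocol 5.6.2.** Reword the bullet so that topical doxepin, gentamicin and neomycin sulfate are prohibited outright, and other topical antibiotics are prohibited except on infected skin as section 5.6.1 permits. The ban on systemic antibiotics and the exclusion list need no change.
- **Protocol 5.6.1.** Make the cross-reference point to Section 5.6.2 alone and drop the mention of the exclusion criteria.
- **Sites and SAP 9.2.** Notify sites, and apply this one rule when judging withdrawals and classifying deviations. If site conduct can no longer change, the classification rule can still be fixed before database lock.

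The cost is one bullet, one cross-reference and a site notice. No new data are needed: under Protocol 5.6 the concomitant medication record already holds the drug name, route and reason for use, so affected subjects can be identified.

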6.1 Medical History, Demography, and Baseline Characteristics

6.1.1 Demographics

For rollover subjects, demographic information collected during the parent study will be used for this study, including age, sex, race, and ethnicity.

For direct-enrolling subjects, demographic information collected will include age, sex, race, ethnicity, and Fitzpatrick skin type. Information on Fitzpatrick skin type can be found in [Appendix 2](#).

6.1.2 Medical History

For rollover subjects, medical, medication, and family history collected during the parent study will be used for this study.

For direct-enrolling subjects, Medical history will be collected to ensure subjects are eligible for participation in the study per inclusion ([Section 4.2](#)) and exclusion ([Section 4.3](#)) criteria. Data collected for direct-enrolling subjects will include year of AD diagnosis, allergic conditions, cardiovascular (CV) medical history and risk factors (including height, weight, blood pressure, medical conditions, and family history of premature CV disease), and family history of liver disease. As part of the direct-enrolling subject's medical history, all systemic (oral and injectable) medications used by the subject for treatment of AD prior to 30 days before the Screening visit will be collected.

For all subjects (rollover subjects and direct-enrolling subjects), if a subject has previously tested positive for COVID-19 or has previously received a COVID-19 vaccine, it should be documented in the subject's medical history.

6.2 Safety Assessments

6.2.1 Adverse Events

All AEs and SAEs will be collected from the time the subject signs the informed consent form (ICF) until the final visit/contact with the subject. AEs that began during the parent study and were ongoing at the end of that study will be reported as ongoing AEs. Additional safety information, including the definition of an AE and the methods for recording, evaluating, and assessing causality of AEs and the procedures for completing and transmitting SAE reports are provided in [Section 8](#).

6.2.2 Brief Physical Examination

A brief physical examination will include, at a minimum, assessments of the skin, lungs, cardiovascular system, and abdomen (liver and spleen). Assess for changes in onset of menses (female participants) or sexual activity (male or female participants). Determine if there is a need for contraception or barrier use. Investigators should pay special attention to clinical signs related to previous serious illness.

For direct-enrolling subjects, height and weight will be measured at Screening only.

6.2.3 Vital Signs

Vital signs will be measured before blood collection for clinical laboratory assessments and will include measurements of systolic and diastolic blood pressure, pulse rate, and body temperature. Subjects should be in a seated position for at least 5 minutes before vital signs measurement.

6.2.4 Clinical Safety Laboratory Assessments

All protocol-required laboratory assessments must be conducted in accordance with the Study Reference Manual or Laboratory Manual and the protocol Schedule of Assessments ([Table 1](#)). Laboratory requisition forms must be completed, and samples must be clearly labeled with the subject number, protocol number, site number, and visit date. Details for the preparation and shipment of samples will be provided by the laboratory and are detailed in the Study Reference Manual or the Laboratory Manual. Reference ranges for all safety parameters will be provided to the site by the laboratory responsible for the assessments.

A list of clinical laboratory tests and parameters is provided in [Table 3](#).

All laboratory tests with values that are considered clinically significantly abnormal during participation in the study should be repeated until the values return to normal or Baseline. If such values do not return to normal within a period judged reasonable by the Investigator, the etiology should be identified, if possible, and the Sponsor and Medical Monitor notified.

Table 3: Laboratory Tests

Diagnostic Tests		

• All subjects
• Urine pregnancy tests (WOCBP only)^a• Direct-Enrolling Subjects Only
• Serum pregnancy test at Screening (WOCBP only)• HBsAg• Hepatitis C antibody• Anti-HBc• Anti-HBs^b• At the Investigator's discretion, subjects may be screened for alcohol and illicit drug use.		
Serum Chemistry		

• BUN• Creatinine• Glucose (fasting not required)• Sodium• Potassium• Chloride	
• Total carbon dioxide• Calcium• AST• ALT• Alkaline phosphatase	
• Uric acid• Total bilirubin (+fractionated if required)• Total protein• Albumin
Hematology		

• Platelet count• RBC count• WBC count (absolute)• Reticulocyte count• Hemoglobin• Hematocrit	
• RBC Indices:
• MCV• MCH• MCHC• Reticulocyte percentage	
• WBC Differential:
• Neutrophils• Lymphocytes• Monocytes• Eosinophils• Basophils

6.3 Efficacy Assessments

To minimize inter observer variability, Investigators and/or evaluators/raters will be trained on each of the required assessments during an Investigator meeting, site initiation visit, and/or utilizing online assessments before enrolling subjects at their study site. Only trained evaluators/raters are permitted to perform the efficacy assessments. To the fullest extent possible, the same Investigator (or designated evaluator/rater) will perform all efficacy assessments for an individual subject throughout the study. If it is not possible for the same evaluator/rater to continue performing assessments, it is recommended that the primary and subsequent evaluator/rater both examine and discuss their respective scoring during at least 1 visit.

6.3.1 Assessments Completed by Investigator

6.3.1.1 Validated Investigator Global Assessment of Atopic Dermatitis

The vIGA-AD™ of disease severity will be assessed at every clinic visit. The vIGA-AD™ is a global assessment of the current state of the disease. It is a 5-point morphological assessment of overall disease severity (scalp excluded) and will be determined according to the categories described in Table 4 and [Appendix 5](#). Eli Lilly and Company developed the vIGA-AD™ scale for use in clinical trials.

Table 4: Validated Investigator Global Assessment Scale for Atopic Dermatitis

Score	Category	Definition
0	Clear	No inflammatory signs of atopic dermatitis (no erythema, no induration/papulation, no lichenification, no oozing/crusting). Post-inflammatory hyperpigmentation and/or hypopigmentation may be present.
1	Almost clear	Barely perceptible erythema, barely perceptible induration/papulation, and/or minimal lichenification. No oozing or crusting.
2	Mild	Slight but definite erythema (pink), slight but definite induration/papulation, and/or slight but definite lichenification. No oozing or crusting.
3	Moderate	Clearly perceptible erythema (dull red), clearly perceptible induration/papulation, and/or clearly perceptible lichenification. Oozing and crusting may be present.
4	Severe	Marked erythema (deep or bright red), marked induration/papulation, and/or marked lichenification. Disease is widespread in extent. Oozing or crusting may be present.

